#### **9.1.3.3 Hepatic function abnormalities (hepatotoxicity)**

Immune-mediated hepatitis/hepatic toxicity is the inflammation of the liver. Hepatic AEs induced by PD-1/PD-L1 inhibitors commonly present as asymptomatic increase of AST and ALT, rarely total bilirubin. A proportion of patients may be presenting with fatigue, fever and radiologic appearances including hepatomegaly, periportal lymphadenopathy and periportal oedema (Zhang et al 2016).

As a grouped term, selected hepatic events including laboratory abnormalities were reported at

a frequency of 15.1% (248 patients) across 1645 patients who have received durvalumab monotherapy 10 mg/kg Q2W. Hepatitis events (autoimmune hepatitis, hepatitis toxic, hepatocellular injury, hepatotoxicity and hepatitis acute) were reported at a frequency rate of Uncommon (14 patients; 0.9%). For 9 of the 14 patients, the events of hepatitis were CTC Grade 3 in severity. There were no Grade 4 events. One patient experienced a CTC Grade 5 event of autoimmune hepatitis. Other AESIs such as hepatic failure (5 patients), jaundice (4 patients) and laboratory abnormality AESIs have been observed, two of which resulted in a fatal outcome (CTC Grade 5 hepatic failure and hyperbilirubinaemia). With the durvalumab + tremelimumab combination patients, there were two reports of hepatitis, 1 CTC Grade 1 hepatitis (1 of 560 patients; 0.2%) and 1 CTC Grade 3 autoimmune hepatitis (0.2%) both of

which were considered treatment-related by the reporting investigator. Additionally, there was 1 report of non treatment-related Grade 2 hepatic failure.

Monitoring liver function tests while receiving study medication is important as hepatitis often manifests as asymptomatic elevated levels of hepatic transaminases (ALT, AST, bilirubin; Kim et al 2013). Prompt treatment with steroids is important as per current established toxicity management guidelines.

In Ipilimumab-treated patients, clinical manifestations of hepatitis included nonspecific symptoms of mild fever, general weakness, fatigue, nausea and/or abdominal pain. In the absence of clinical symptoms, treatment-emergent hepatitis presented asymptotically as elevated hepatic transaminases. Ultrasonograms of the liver can appear normal or may demonstrate homogenous hepatomegaly, edema, or enlarged perihepatic lymph nodes. Biopsy of the liver most commonly shows a diffuse T-cell infiltrate. Other reported pathology patterns include inflammation focused around either hepatocytes or bile ducts.

If subject presents with liver dysfunction, a high suspicion for irAE hepatitis is warranted, however, it is important to distinguish treatment-related toxicity and rule out other causes of hepatic injury, such as infection, preexisting medical conditions, immunosuppression, metabolic or cardiovascular derangements, other medications, or tumor progression.

#### **9.1.3.4 Rash/Dermatitis**

Immune-mediated dermatitis is generally mild and presents as mild local or diffuse maculopapular, erythematous rash on the trunk or extremities, which may be accompanied by pruritus, alopecia, and vitiligo, suggestive of inflammatory response to melanocytes

Clinical Study Protocol

Drug Substance Tremelimumab

Study Number **ESR-14-10744**

Edition Number 8

Date 17 April 2019

(Lacouture et al 2014). In rare cases, severe dermatitis has been reported to manifest as Stevens-Johnson syndrome, toxic epidermal necrolysis, or rashes complicated by dermal ulceration or necrotic, bullous, or haemorrhagic manifestations (Tarthini 2013, Kaehler et al 2010).

AESIs of rash (as a composite term) were reported as Very common in 199 (12.1%) patients receiving durvalumab monotherapy and Very common in 124 (22.1%) patients receiving the combination. The majority of events were CTC Grade 1 or 2, with 7 and 4 patients, respectively, experiencing CTC Grade 3 events.

AESIs falling under the grouped term of dermatitis that include milder events such as pruritus, eczema and erythema to more specific or severe skin toxicities such as events of dermatitis bullous, dermatitis exfoliative or dermatitis psoriasiform, have been observed with durvalumab monotherapy. Overall, the range of these events have been reported at a frequency of Very common (n=237; 14.4%) in monotherapy treated patients and patients receiving durvalumab + tremelimumab combination (n=114; 20.4%). However, most events were CTC Grade 1 in severity with 3 patients and 4 patients experiencing CTC Grade 3 events in the monotherapy and combination treated groups respectively.

Prompt treatment with steroids (topical or systemic based on severity) is important as per current established toxicity management guidelines.

Pathologic evaluations of biopsy specimens of affected skin often demonstrate eosinophilic infiltration or leukocytoclastic vasculitis; or, they may reveal a lymphocytic predominance characterized by CD8+ T cells, sometimes with tropism for melanin-containing cells. Specifically, in metastatic melanoma patients, the rash associated with immune-checkpoint inhibitors may be indicative of immune response to melanocytes and may progress to vitiligo in some cases. Biopsies showed severe dermatitis with papillary dermal edema, sometimes accompanied by perivascular lymphocytic infiltrate.

Guidelines for the management of subjects with immune-mediated events including dermatitis are outlined in Section 6.6.1.

### **9.1.3.5 Colitis**

Diarrhoea is the most frequent AESI reported across the Phase I to Phase III clinical studies with durvalumab monotherapy, as of the DCO dates for this IB with a frequency of Very common (263/1645; 16.0%) in patients receiving 10 mg/kg durvalumab iv Q2W. Most of these were CTC Grade 1 in severity. Treatment-emergent colitis-type AESIs were reported at a

frequency of Common (16 of 1645 patients; 1.0%). Most were CTC Grade 2 or 3. CTC Grade 4 colitis was reported in 1 patient (rare; <0.1%).

In the durvalumab + tremelimumab combination in patients receiving 20 mg/kg durvalumab iv Q4W and 1 mg/kg tremelimumab, diarrhoea was reported at a frequency of Very common (144/560; 25.7%) with most CTC Grades 1 or 2. Colitis was reported at a frequency of Common (26/560; 4.6%). Most colitis events were CTC Grade 3 reported in 17 of the 26 patients on the combination. There were no CTC Grade 4 or 5 cases reported in the combination patients. Patients should be monitored for signs and symptoms of colitis or diarrhoea.

Investigators are instructed to begin diarrhoea management early to minimise the risk of colitis (please refer to the toxicity management guidelines in the study protocols). Early initiation of diarrhea treatment guidelines has been shown to reduce bowel perforation and colectomy rates, drug-related diarrhoea, and serious gastrointestinal imAEs by up to 50% in patients treated with ipilimumab (Tanhini 2013).

#### **9.1.3.6 Endocrinopathy (hypothyroidism, hyperthyroidism, hypopituitarism)**

Immune-mediated endocrinopathy is the inflammation of any organ in the hypothalamic pituitary- adrenal axis, but is most typically reported to affect the pituitary, thyroid and/or adrenal glands in patients treated with checkpoint inhibitors, leading to hypophysitis/hypopituitarism, thyroid dysfunction, and/or adrenal insufficiency (Teply and Lipson 2014). The clinical presentation of immune-mediated endocrinopathies most often include hypothyroidism, hyperthyroidism, and nonspecific symptoms of headache and fatigue, but may also include myalgias, visual field defects, behavioural changes, electrolyte disturbances, loss of appetite and hypotension (Tanhini 2013). Patients will generally have abnormal endocrine laboratory test results that include thyroid-stimulating hormone, free T4, total and free T3, cortisol, adrenocorticotropic hormone, luteinising hormone, folliclestimulating hormone, and testosterone.

Most endocrinopathy events reported were CTC Grade 1 or 2. In the monotherapy pool CTC Grade 3 events consisted of adrenal insufficiency (2 patients), hypophysitis/hypopituitarism (1 patient), hyperthyroidism (1 patient) and hypothyroidism (2 patients). There were no CTC Grade 4 or 5 events. In the combination pool there was a slightly increased incidence of higher-grade events of adrenal insufficiency with 3 patients experiencing CTC Grade 3 and 1 patient with CTC Grade 4 in severiyy. There was 1 patient with CTC Grade 3 hyperthyroidism and 1 patient with CTC Grade 3 hypophysitis/hypopituitarism.

Prompt initiation of hormone replacement therapy is important for hypothyroidism. Additional guidance for other types of endocrinopathies is provided in the toxicity management guidelines.

### **Nephritis**

The major clinical syndromes produced by immune-mediated renal injury include nephrotic syndrome, rapidly progressive glomerulonephritis, and acute renal failure (Cunard and Kelly 2003). In association to immune-checkpoint inhibitors, two different forms of ipilimumab-induced renal damage are reported, acute kidney injury due to predominant acute granulomatous tubulointerstitial nephritis and nephrotic syndrome in lupus nephritis (Izzedine et al 2014). Signs and symptoms include increase in serum creatinine, decrease in urine output, peripheral oedema, haematuria, loss of appetite.

As a grouped term, selected renal events including laboratory abnormalities were reported at a

frequency of 5.3% (87 patients) across the 1645 patients included in the durvalumab monotherapy pool. Nephritis events were reported at a frequency rate of Uncommon (5 patients; 0.3%) with 1 CTC Grade 2 autoimmune nephritis, 1 CTC Grade 2 glomerulonephritis, 2 CTC Grade 2 nephritis and 1 CTC Grade 3 tubulointerstitial nephritis. There was 1 CTC Grade 3 nephritis reported in the 560 (0.2%; Uncommon) patients in the durvalumab + tremelimumab combination pool. An additional AESI of acute kidney injury was reported in 26 patients (1.6%) receiving durvalumab monotherapy and 7 patients (1.3%) in the combination pool, 1 of which was CTC Grade 5 in severity; the event was considered not treatment-related by the reporting investigator.

Patients should be monitored for changes in renal function (eg, that manifest as elevated serum blood urea nitrogen and creatinine, decreased creatinine CL, electrolyte imbalance, decrease in urine output, or proteinuria and any other findings that may be indicative of nephritis) prior to and periodically during treatment. Prompt treatment with steroids is important as per current established toxicity management guidelines in the study protocols.

#### **9.1.3.7 Neuropathy/Neuromuscular Events (to include MG and GB)**

Neuromuscular toxicity is relatively uncommon but may manifest as a mild peripheral sensory neuropathy or muscle weakness. Although they are rare, severe neuropathies and myopathies have been observed. Emergent cases of neuropathy can present with Guillain-Barré syndrome, transverse myelitis, or myasthenia gravis, among other diagnoses. Depending on presentation, patients may require neuroimaging, nerve conduction studies, and, potentially, nerve or muscle biopsy to arrive at the diagnosis (Teply and Lipson 2014). Isolated cases of myasthenia gravis have been reported in studies combining anti-PD-1/PD-L1 mAb with anti-CTLA-4 mAb ( Naidoo et al 2015).

As of the DCO for this IB there have been no reports of Guillain-Barre syndrome or Myasthenia Gravis in patients receiving durvalumab monotherapy. Two patients receiving the durvalumab + tremelimumab combination have reported a case of Myasthenia Gravis but none at the recommended dose of 20 mg/kg durvalumab iv Q4W and 1 mg/kg tremelimumab.

Prompt treatment of these conditions as per current toxicity management guidelines is important. Patients should be monitored for signs and symptoms that may include peripheral sensory neuropathy, muscle weakness, peripheral neuropathy including numbness, tingling, and sensitivity to touch.

Neuropathies associated with ipilimumab have been difficult to assess because these irAEs are transient and present with vague symptoms. Presentations of neurotoxicity may include a mild peripheral sensory neuropathy or muscle weakness. Symptoms of peripheral neuropathy

include numbness, tingling, paresthesia (pins and needles sensations), sensitivity to touch, or muscle weakness. In patients with extreme symptoms, they may present with burning pain, muscle wasting, paralysis, or organ dysfunction. Symptoms are typically detected with physical examination findings ranging from sensory changes to loss of deep-tendon reflexes.

Depending on presentation, patients may require neuroimaging, nerve conduction studies, and, potentially, nerve or muscle biopsy to arrive at the diagnosis.

## **Pancreatitis**

Pancreatitis is an inflammatory condition of the pancreas that typically manifests initially as asymptomatic elevations of amylase and lipase in patients treated with immune checkpoint inhibitors. Clinical presentation frequently includes low-grade abdominal pain with accompanying fever and malaise (Weber et al 2012, Di Giacomo et al 2010). Biopsies showed diffuse T-cell infiltrate consistent with immune-mediated pancreatitis (Weber et al 2012).

Across the 1645 patients in the monotherapy program, events of pancreatitis were Uncommon to rare. Two patients (0.1%) experienced pancreatitis (CTC Grade 3 and Grade 4 in severity) and 1 patient (<0.1%) with CTC Grade 3 acute pancreatitis. Elevations in amylase and lipase were reported at a frequency rate of Common (0.4% and 0.4%, respectively). In ongoing sponsored studies with durvalumab + tremelimumab therapy in 560 patients, events of pancreatitis were Uncommon; pancreatitis was reported in 4 patients (0.7%) with 3 of these CTC Grade 3 in severity and acute pancreatitis in 1 patient (0.2%). Elevations in amylase and lipase were reported at a frequency of Common (6.1% and 7.0%, respectively). Patients should be monitored for signs and symptoms of pancreatitis including Grade 3 or 4 elevations in lipase and/or amylase.

Prompt treatment of this condition as per current established toxicity management guidelines is important.

## **Other Potential Risks**

### **Serious Infections**

Serious and/or  $\geq$  Grade 3 infections requiring hospitalisation including, but not limited to, sepsis, pneumonia, lung infections, have been reported in clinical studies with durvalumab, but are often confounded by underlying disease and use of concomitant medications (ie, steroids and other immunosuppressives) that may cause opportunistic infections. As of the DCO, events from the MedDRA Infections and Infestations SOC, events with a severity  $\geq$ Grade 3 and frequency of  $\geq$ 1% included lung infection (n=16; 1%), pneumonia (n=39; 2.4%), sepsis (n=26; 1.6%) and urinary tract infection (n=20; 1.2%). CTC Grade 3 events were reported in 98 patients (6.0%), CTC Grade 4 events were reported in 25 patients (1.5%) and CTC Grade 5 infection events in 15 patients (0.9%). Across the durvalumab + tremelimumab combination program, patients experiencing  $\geq$ Grade 3 infections at a frequency

Clinical Study Protocol

Drug Substance Tremelimumab

Study Number **ESR-14-10744**

Edition Number 8

Date 17 April 2019

of  $\geq 1\%$  included lung infection (n=9; 1.6%), pneumonia (n=14; 2.5%), sepsis (n=6; 1.1%) and urinary tract infection (n=9; 1.6%). CTC Grade 3 events were reported in 50 patients (8.9%), CTC Grade 4 events were reported in 2 patients (0.4%) and CTC Grade 5 infection events in 4 patients (0.7%). Patients should be monitored for serious infections while receiving durvalumab.

## **9.2 Assessment of safety parameters**

### **9.2.1 Assessment of severity**

Severity will be graded according to the NCI CTCAE v4.03. The determination of severity for all other events not listed in the CTCAE will be made by the investigator based upon medical judgment and the severity categories of Grade 1 to 5 as defined below.

Grade 1 (mild)	An event that is usually transient and may require only minimal treatment or therapeutic intervention. The event does not generally interfere with usual activities of daily living.
Grade 2 (moderate)	An event that is usually alleviated with additional specific therapeutic intervention. The event interferes with usual activities of daily living, causing discomfort but poses no significant or permanent risk of harm to the subject.
Grade 3 (severe)	An event that requires intensive therapeutic intervention. The event interrupts usual activities of daily living, or significantly affects the clinical status of the subject.
Grade 4 (life threatening)	An event, and/or its immediate sequelae, that is associated with an imminent risk of death or with physical or mental disabilities that affect or limit the ability of the subject to perform activities of daily living (eating, ambulation, toileting, etc.).
Grade 5 (fatal)	Death (loss of life) as a result of an event.

It is important to distinguish between serious criteria and the severity of an AE. Severity is a measure of intensity whereas seriousness is defined by the criteria in Section 10.1.2. A Grade 3 AE need not necessarily be considered an SAE. For example, a Grade 3 headache that persists for several hours may not meet the regulatory definition of an SAE and would be considered a nonserious event, whereas a Grade 2 seizure resulting in a hospital admission would be considered an SAE.

### **9.2.2 Assessment of relationship**

In this study, patients will receive one infusion of MEDI4736 either alone or in combination with tremelimumab. The remaining procedures to be conducted in this study will follow standard of care for the treatment of patients with surgically resectable MPM. The study investigators will carefully monitor subjects to determine whether adverse events are related to the infusion of study drug or are expected complications of standard clinical procedures.

### **9.3 Recording of adverse events and serious adverse events**

Adverse events associated with the investigational product will be recorded in an adverse event log maintained by the principal investigator using a recognized medical term or diagnosis that accurately reflects the event. Adverse events associated with the investigational product will be assessed by the investigator for severity, relationship to the investigational product, possible etiologies, and whether the event meets criteria of an SAE and therefore requires immediate notification to AstraZeneca/MedImmune Patient Safety.

The following variables will be collected for each AE associated with the investigational product:

- AE (verbatim)
- The date when the AE started and stopped
- Changes in NCI CTCAE grade and the maximum CTC grade attained
- Whether the AE is serious or not
- Investigator causality rating against MEDI4736 (yes or no), tremelimumab (yes/no)
- Action taken with regard to MEDI4736/tremelimumab
- Outcome

In addition, the following variables will be collected for SAEs associated with the investigational product as applicable:

- Date AE met criteria for serious AE
- Date Investigator became aware of serious AE
- AE is serious due to
- Date of hospitalization
- Date of discharge
- Probable cause of death

- Date of death
- Autopsy performed
- Description of AE
- Causality assessment in relation to Study procedure(s)

Causality assessment in relation to tremelimumab

Events that are unequivocally due to disease progression will not be reported as an AE during the study.

### **9.3.1 Study recording period and follow-up for adverse events and serious adverse events**

Adverse events and serious adverse events associated with the investigational product will be recorded from the time of signature of informed consent, throughout the treatment period and including the follow-up period (90 days after the last dose of MEDI4736).

During the course of the study all AEs and SAEs associated with the investigational product will be proactively followed up for each subject. Every effort will be made to obtain a resolution for all events, even if the events continue after discontinuation/study completion.

If a subject discontinues from treatment for reasons other than disease progression, and therefore continues to have tumor assessments, drug-related SAEs must be captured until the patient is considered to have confirmed PD and will have no further tumor assessments.

The investigator is responsible for following all SAEs associated with the investigational product until resolution, until the subject returns to baseline status, or until the condition has stabilized with the expectation that it will remain chronic, even if this extends beyond study participation.

#### **Follow-up of unresolved adverse events**

Any AEs associated with the investigational product that are unresolved at the subject's last visit in the study are followed up by the investigator for as long as medically indicated, but without further recording in the adverse event log. After 90 days, only subjects with ongoing investigational product-related SAEs will continue to be followed for safety.

AstraZeneca/MedImmune retains the right to request additional information for any subject with ongoing AE(s)/SAE(s) associated with the investigational product at the end of the study, if judged necessary.

## **Post study events**

After the subject has been permanently withdrawn from the study, there is no obligation for the investigator to actively report information on new AE or SAEs associated with the investigational product occurring in former study subjects after the 90-day safety follow-up period for patients treated with MEDI4736 or MEDI4736 + tremelimumab. However, if the investigator learns of any SAEs associated with the investigational product, including death, at any time after the subject has been permanently withdrawn from study, and he/she considers there is a reasonable possibility that the event is related to study treatment, the investigator will notify the study sponsor and AstraZeneca/MedImmune Drug Safety.

### **9.3.2 Reporting of adverse events**

Any adverse events or toxicities that are determined to be related to surgery should NOT be reported unless they are unusual.

Such AEs common following surgical resection by EPP or PD can occur within the hospital stay immediately following surgery, or can persist once the patient is discharged and seen in the outpatient clinic postoperatively. Such AEs may include:

- 1) Chest pain or incisional pain
- 2) Hypotension (including orthostatic hypotension)
- 3) Tachycardia
- 4) Atrial fibrillation (or other atrial arrhythmia)
- 5) Dyspnea
- 6) Anorexia, or loss of appetite
- 7) Anemia
- 8) Hyponatremia
- 9) Hypernatremia
- 10) Hypokalemia

- 11) Hyperkalemia
- 12) Hypomagnesemia
- 13) Increased creatinine
- 14) Leukocytosis
- 15) Acidosis

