### **9.1.1 Safety Parameters**

#### **9.1.1.1 Definition of adverse events**

The International Conference on Harmonization (ICH) Guideline for Good Clinical Practice (GCP) E6 (R1) defines an AE as:

Any untoward medical occurrence in a patient or clinical investigation subject administered a pharmaceutical product and which does not necessarily have a causal relationship with this treatment. An AE can therefore be any unfavorable and unintended sign (including an abnormal laboratory finding), symptom, or disease temporally associated with the use of a medicinal product, whether or not considered related to the medicinal product.

An AE includes but is not limited to any clinically significant worsening of a subject's pre-existing condition. An abnormal laboratory finding (including ECG finding) that requires an action or intervention by the investigator, or a finding judged by the investigator to represent a change beyond the range of normal physiologic fluctuation, should be reported as an AE.

Adverse events may be treatment emergent (i.e., occurring after initial receipt of investigational product) or nontreatment emergent. A nontreatment-emergent AE is any new sign or symptom, disease, or other untoward medical event that begins after written informed consent has been obtained but before the subject has received investigational product.

Elective treatment or surgery or preplanned treatment or surgery (that was scheduled prior to the subject being enrolled into the study) for a documented pre-existing condition, that did not worsen from baseline, is not considered an AE (serious or nonserious). An untoward medical

Clinical Study Protocol

Drug Substance Tremelimumab

Study Number **ESR-14-10744**

Edition Number 8

Date 17 April 2019

event occurring during the prescheduled elective procedure or routinely scheduled treatment should be recorded as an AE or SAE.

The term AE is used to include both serious and non-serious AEs.

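### The adverse-event definition, log and surgical reporting rule do not fit together, leaving it unclear whether serious events attributed to surgery are reported

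*Combined protocol and SAP*

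**What the plan says.** **Definition (Section 9.1.1.1).** An adverse event is one that "does not necessarily have a causal relationship with this treatment". A non-treatment-emergent event is one that "begins after written informed consent has been obtained but before the subject has received investigational product". For planned procedures, an untoward "event occurring during the prescheduled elective procedure or routinely scheduled treatment should be recorded as an AE or SAE". The section closes: "The term AE is used to include both serious and non-serious AEs".

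**Serious events (Section 9.1.2).** These may arise in any study phase. The investigator assesses their relationship to all study treatment and procedures and passes the assessment to the company.

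**The log (Sections 9.3 and 9.3.1).** "Adverse events associated with the investigational product will be recorded in an adverse event log maintained by the principal investigator". Recording starts when consent is signed and ends 90 days after the last dose of MEDI4736. For serious events, one of the variables collected is causality against study procedures.

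**The surgical rule (Section 9.3.2).** "Any adverse events or toxicities that are determined to be related to surgery should NOT be reported unless they are unusual". The section adds that common post-operative events "can persist once the patient is discharged and seen in the outpatient clinic postoperatively", and lists 15 that may occur.

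**Reporting of serious events and deaths (Sections 9.3.3 and 9.3.3.1).** Section 9.3.3 covers product-associated serious events, whether or not they are thought to be caused by the product. Section 9.3.3.1 covers all deaths on study or within 90 days of the last dose. If a death is not clearly due to progression, the causal event is a serious event to be reported within 24 hours. Deaths of unknown cause are always reported as serious.

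**Elsewhere.** The Synopsis (Safety Assessments) follows subjects for any adverse event for 90 days. Section 7 describes the same follow-up as being for events related to the study drug.

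**The concern.** Four sections set the scope of safety capture, and each sets it differently. Site staff cannot follow all of them. The rule with the clearest instruction, Section 9.3.2, makes attribution a condition for reporting when it should be one of the things reported.

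The attribution is made by an investigator who knows the treatment (Section 5.4.1) and who is asked to separate drug effects from expected surgical complications (Section 9.2.2). The drug-safety window overlaps heavily with surgical recovery, and several of the listed events are also described in the protocol as signs of immune-mediated toxicity. If an event is judged surgical, and the log is read as holding only drug-related events, the trial database may hold nothing to re-examine should that judgement later be questioned.

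**Working it through.** The plan gives no figure to reproduce. The check sets the sections side by side for five kinds of event, followed by one piece of arithmetic.

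**Two readings of the log.** Sections 9.3 and 9.3.1 do not say whether association with the product is causal (thought to be due to it) or temporal (occurring after it was given).

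1. *Event after consent but before dosing.* An adverse event under Section 9.1.1.1, and inside the recording period of Section 9.3.1. It cannot be associated with a product not yet given, so the log misses it on either reading.
2. *Non-serious post-operative event judged surgical, treated patient.* Causal reading: not logged. Temporal reading: logged. Section 9.3.2 bars reporting unless the event is unusual. Recording and not reporting can coexist, but only on the temporal reading.
3. *Serious post-operative event judged surgical, treated patient.* Section 9.1.2 points toward capture. Section 9.3.3 is ambiguous, because it requires association and then sets causality aside. Section 9.3.2 taken literally says no: it covers any adverse event, Section 9.1.1.1 says that term includes serious ones, and there is no seriousness or grade limit and no cross-reference to Sections 9.1.2, 9.3.3 or 9.3.3.1. The answer is unclear.
4. *Death attributed to surgery.* Section 9.3.3.1 requires reporting and makes no surgical exception. The answer is clear.
5. *Event in a control.* The Schedule of Study Assessments includes adverse-event assessment and Section 9.3.1 starts recording at consent. The period ends 90 days after a dose that controls never receive, so they have no end date. How the association criterion applies to them is not stated.

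**Share of the safety window that is post-operative.**

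- Safety window: 90 days after the last dose (Synopsis, Safety Assessments; Section 9.3.1). There is only one dose.
- Infusion to resection: one to six weeks, so t = 7 to 42 days (Section 3.1).
- Post-operative days = 90 − t; share = (90 − t) / 90.
- t = 7: 90 − 7 = 83 days; 83 / 90 = 92%.
- t = 42: 90 − 42 = 48 days; 48 / 90 = 53%.

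**Shared signs.** Of the events listed in Section 9.3.2, dyspnea is named for pneumonitis (Section 9.1.3.1), hypotension and loss of appetite for endocrinopathy (Section 9.1.3.6), and increased creatinine for nephritis (the Nephritis heading that follows).

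**The case against.** The best defence is that the association in Sections 9.3 and 9.3.1 is temporal. Section 9.1.1.1 itself speaks of events temporally associated with use of a product. Section 9.3 then asks for relationship, possible etiologies and a yes/no causality rating, fields that would be largely redundant if only drug-caused events were logged. On that reading post-dose surgical events do enter the log. This stands as a credible reading, so it cannot be said that the log certainly excludes them. It does not rescue pre-dose events, and the protocol does not say which reading applies.

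It is also fair that Section 9.1.1.1 speaks of recording events during a procedure, whereas Section 9.3.2 speaks of reporting events in the post-operative period. The direct clash between those two sections is therefore narrow.

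Safeguards exist. Appendix 1 (General Considerations) has events without a clear alternative cause managed as immune related, and Section 9.1.3 requires rapid communication of events of special interest. Both depend on the same judgement, and recent surgery is a ready alternative cause. Hospital records would still exist, though not as trial data. No between-arm safety comparison is planned, so no planned analysis is damaged.

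A reader might infer more than the documents support:

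- *Surgical deaths go unreported.* Section 9.3.3.1 requires them.
- *Serious surgical events are plainly excluded.* Section 9.1.2 points the other way; the position is ambiguous.
- *Controls have no adverse events recorded.* Assessments are scheduled and recording starts at consent; the gaps are the missing end date and the undefined association.
- *Toxicity is being misclassified.* Shared symptoms do not show this. Section 9.3.2 is triggered by a judgement that surgery was the cause, not by a symptom being on the list.

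**Conclusion.** The inconsistency is real and should be corrected. Pre-dose events fall outside the log on any reading, controls have no end of capture, unusual has no working definition, and the reportability of a serious event attributed to surgery cannot be settled from the text.

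The surgical rule can operate on 48 to 83 of the 90 safety days (53% to 92%) in treated patients who undergo resection. This assumes resection within the planned one to six weeks and counts all time after surgery, since Section 9.3.2 extends past discharge and sets no end. It is time exposed to the rule. The documents give no basis for estimating how many events, if any, would be lost. The primary CD8/Treg analysis does not depend on any of this.

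**What to change.** Reconcile the Synopsis (Safety Assessments) and Sections 7, 9.1.1.1, 9.1.2, 9.3, 9.3.1, 9.3.2, 9.3.3 and 9.3.3.1, as follows:

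- Log all adverse events from consent in all three arms, with a stated end date for controls.
- Keep attribution (drug, surgery, disease) as a recorded field, not a condition for entry.
- Limit the list in Section 9.3.2 to non-serious events that are recorded but need no expedited report, and define or remove unusual.
- State that a listed event meeting any seriousness criterion follows Section 9.3.3, and that deaths follow Section 9.3.3.1.
- Say what association with the investigational product means wherever it sets scope, including in Section 9.3.3 beside the clause on causality.

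The cost is protocol wording and entry of more expected post-operative events for 20 patients at one site. Listings by arm would remain descriptive at 8, 8 and 4 patients. Recording does not correct a wrong attribution; it leaves something that can be reviewed.
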